Second experimental session day: During the second experimental session day, participants will be lying down in a supine position within an MRI scanner during administrations of placebo (inhaled air) and a 15 or 12 µg/kg dose of salvinorin A (whichever dose did not yield erratic movement during the first experimental session). Participants will be told that they are being continuously monitored by an intercom and can stop the scan at any time, but that it is best for them to remain still and refrain from any head, face or jaw movements. Participants will also be told that a study team member will remain in the scanner room with them throughout the procedures. The placebo condition (inhaled air) will always precede the salvinorin A condition. MRI scans will be used to obtain structural brain images, as well as functional data that permit the direct measurement of oxygenated blood (using blood-oxygenation level dependent [BOLD] techniques) to assess acute effects of salvinorin A on brain function. Heart rate (via pulse oximetry), respiration, and end-tidal carbon dioxide may also be collected in order to correct for artifacts in BOLD signal. BOLD signal data will be collected during two 20 minute scans (one scan for placebo and one scan for salvinorin A). During each scan, an inhalation period will begin 30 seconds after the beginning of BOLD data collection, and will be cued via audio stimulus using MR-safe headphones. A study team member will be present in the scanner room with the volunteer during scanning and inhalation procedures, to provide support to the participant during procedures. Participants will be told that one of the inhalations will be the dose of salvinorin A that they received during the first session, and the other inhalation will be either a placebo or a variable dose of salvinorin A, but no dose of salvinorin A higher than the dose they received during the first session will be administered.

All imaging procedures will be performed using 3T Siemens MRI scanner at the MRI Research Service Center at Johns Hopkins Hospital, by individuals specifically trained in these procedures. MRI assessments

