involve standard methods and established pulse sequences utilized in research evaluations and do not involve the injection of any contrast or other invasive procedures. We will work closely with the neuroimaging experts in the MRI Research Service Center to ensure safe and effective implementation of the tasks conducted in the scanner. [name], the principle investigator on the team, has extensive experience with brain imaging and is currently leading MRI and PET neuroimaging studies of the acute effects of the classic hallucinogen psilocybin. [name] will oversee the development and conduct of brain imaging procedures and analysis of the resulting data.

After completing the scanning procedures, the participant will complete brief (e.g., 10-15 minute) behavioral measures and/or questionnaires regarding the subjective effects that they experienced during the scanning session. These measures will be used along with ratings made in the scanner to interpret differences in brain activation between participants and across conditions. For example, changes in brain activation may be correlated with ratings of subjective effects (e.g. the Mystical Experience Questionnaire, or the Challenging Experience Questionnaire) experienced during the scanning procedures. Subjects will also be asked to write a narrative description of the experience of each salvinorin A session within about one week after a session.

Participants will undergo drug administration during collection of BOLD signal in the MRI. Real-time fMRI analysis techniques may be employed to monitor volunteer head motion as the scans are collected. If participants exhibit gross (> 1mm of movement in any plane) frequent (for more than 25% of the scan time) head motion, we may repeat the given drug administration and scan, since frequent gross motion may invalidate BOLD imaging data (Power, Barnes, Snyder, Schlaggar, & Petersen, 2012; Power et al., 2014). We may repeat drug administration and scanning up to two times. No more than one salvinorin A administration will occur on a single day. Repeated administrations of salvinorin A may occur on consecutive days.

Schedule of Events for Second Experimental Session Day

Time Point (minutes from drug administration)	Procedure	Description
-65 (or more)	Intake procedures	Participant will complete drug and pregnancy urine tests, and complete a pre-session questionnaire to assess the psychological “set” of the volunteer (including mood state and cognitive state)

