-40 (approximate)	Setup	The participant will be brought to the MRI suite. The prepared salvinorin A dose for this participant and session will be brought from the BPRU pharmacy to the MRI suite. All materials and equipment for drug delivery and study monitoring will be set up, including passing the non-ferromagnetic inhalation tube through the pass-through panel from the MRI control room to the MRI scanning room. The volunteer will be placed in a head-first supine position on the scanner bed, with the head placed within the MRI head coil. The volunteer will be provided with MR-safe earbud head phones that provide hearing protection, as well as additional padding to prevent head movement and further provide hearing attenuation, consistent with standard MRI procedures. The inhalation tubing will be taped on to the MRI head coil in a position that is accessible to the volunteer, and the volunteer will be moved into the magnet. A study team member will remain with the volunteer in the MRI scanning room throughout the procedures. Structural scanning procedures will then commence.
-20	Placebo scan	A 20-minute EPI scanning sequence will be started, and placebo inhalation will begin 30 seconds after the start of the EPI scan. The participant will be instructed via inserted MR-safe earbud headphones to begin the inhalation procedure.
0	Salvinorin A scan	After verbally confirming that the volunteer is comfortable and ready to continue, a 20-minute EPI scanning sequence will be started, and salvinorin A inhalation will begin 30 seconds after the start of the EPI

		scan. The participant will be instructed via inserted MR-safe earbud headphones to begin the inhalation procedure.
20	Scan end	After the salvinorin A scan has completed, the volunteer will be removed from the MRI and brought to a private adjacent room and verbally debriefed.
25	Final Questionnaires	The participant will be asked to complete brief (10-15 minute) behavioral measures and/or questionnaires regarding the subjective effects that they experienced while in the scanner.

The schedule of events for the second experimental session day is approximate, but the listed events will always occur in the same sequence.

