Using the lower (more conservative) of the two effect sizes from our previous psilocybin and salvinorin A studies ($d = 0.89$), and an alpha of 0.05, 6 volunteers would be sufficient to detect effects on ratings of drug intensity with 95% power. Empirical and simulation studies have provided recommendations for sample size of imaging experiments (Zandbelt et al., 2008). For similar parameters, including an effect size of 0.89, alpha of 0.05, and 80% power, 21 participants are necessary to power an ROI-based analysis of effects on brain activity similar to behavioral effects of psilocybin. Far fewer participants would be necessary to detect effects similar to the behavioral effects of salvinorin A, though no specific sample size recommendations were made by Zandbelt and colleagues for such a large effect size ($\eta^2 = 0.81$, equivalent to $d > 4$). Thus, the proposed study of 20 participants would be powered to detect clinically significant differences in brain activity between placebo and salvinorin A conditions. Given that consent will be obtained at the initial in-person screening interview, we are requesting approval to consent up to a total of 200 volunteers.

MRI data analyses: MRI data will be preprocessed using standard methods. The time course of brain regions in standard brain atlases (e.g. Chen Atlas or Power Atlas) will be extracted and submitted to functional connectivity analysis.

Statistical analysis of behavioral data: Baseline demographic data will be summarized with descriptive statistics to describe the volunteer population. For measures assessed at multiple time-points, including subjective effects ratings, both time-course and peak-effect data will be examined. For outcomes assessed at screening and one week after the final salvinorin A session, a paired t-test will be used to assess change from baseline (screening). Behavioral measures (including monitor ratings, subjective effects ratings, and questionnaire data) will be correlated with brain-imaging outcome measures to investigate the relationship between individual differences in subjective drug response and individual differences in neural drug response.

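### The post-scan questionnaires ask about the whole scanner stay, so as worded they do not separate the response to salvinorin A from the response to inhaled air

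*Combined protocol and SAP*

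**What the plan says.** The Schedule of Events for Second Experimental Session Day runs in a fixed sequence: structural scanning, the air scan from -20 minutes, the salvinorin A scan from 0, scan end at 20, and Final Questionnaires at 25. At that last entry the participant is to complete "behavioral measures and/or questionnaires regarding the subjective effects that they experienced while in the scanner". The only event listed between the two scans is a verbal check that the volunteer is comfortable and ready.

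The narrative section on the second experimental session day gives the same timing, "After completing the scanning procedures, the participant will complete brief (e.g., 10-15 minute) behavioral measures and/or questionnaires", and a similar recall period, "regarding the subjective effects that they experienced during the scanning session". It names the Mystical Experience and Challenging Experience Questionnaires as examples of ratings that may be correlated with changes in brain activation. It then states the use: "These measures will be used along with ratings made in the scanner to interpret differences in brain activation between participants and across conditions".

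The same section says participants will be told that one inhalation is the dose from their first session and that "the other inhalation will be either a placebo or a variable dose of salvinorin A".

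Under Statistical analysis of behavioral data, behavioral measures are to be correlated with imaging outcomes to study "the relationship between individual differences in subjective drug response and individual differences in neural drug response". The secondary objective, at the start of the protocol, likewise concerns subjective effects of salvinorin A. The primary outcome compares brain activity and connectivity under salvinorin A with the preceding air condition.

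**The concern.** The two variables to be correlated do not have the same reference. The imaging measure contrasts salvinorin A with air. The questionnaire, as worded, asks about everything felt in the scanner and does not ask the participant to divide it by inhalation.

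A participant who has been told that both inhalations might contain drug has good reason to include the air scan in the answer. Unease from confinement, from the air inhalation or from waiting for the drug could raise a challenging-experience score and then be read as drug response. The same reactions may also alter the air scan that is subtracted in the imaging contrast, so the two variables could share variation that is not due to drug.

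What is at stake is the interpretation of a secondary objective. The primary imaging outcome is not affected. Attribution to one inhalation cannot be recovered afterwards from a form that never asked for it.

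**Working it through.** The plan states no figure on this point, so there is none to reproduce. The check has three parts.

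**1. Clock.** Inputs are from the scan-day schedule, whose times are approximate. Each inhalation begins 30 seconds after its scan starts.
- Air inhalation: -20 + 0.5 = -19.5 min. Salvinorin A inhalation: 0 + 0.5 = 0.5 min.
- Questionnaires at 25 min: 25 - (-19.5) = 44.5 min after air, and 25 - 0.5 = 24.5 min after salvinorin A.

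There is one collection point for two conditions, after both.

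**2. Wording side by side.**

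| Item | Reference given |
|---|---|
| First-session questionnaires (minute 45) | acute effects of salvinorin A |
| Timed drug-strength ratings | after each drug inhalation, first session day only |
| Written narrative | each salvinorin A session |
| Scan-day questionnaires | time in the scanner, or the scanning session |
| Ratings made in the scanner | no instrument, time points or schedule entry |

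Elsewhere the authors tie a measure to the drug or to a drug session. The scan-day forms lack that anchor. The first session had no air condition, so the distinction first matters on the scan day.

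**3. Illustration of size. All values are assumed; the documents give none.** Let D be a participant's response to the salvinorin A inhalation and P the response to air. Take D and P as independent, with k = SD(P)/SD(D). A form covering the whole stay yields S = wD + (1 - w)P, where w is the weight the participant gives to the drug period. Its correlation with the drug-minus-air response is

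corr(S, D - P) = [w - (1 - w)k²] / [√(w² + (1 - w)²k²) × √(1 + k²)].

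Example, w = 0.5 and k = 0.5: numerator 0.5 - 0.5 × 0.25 = 0.375; denominator √0.3125 × √1.25 = 0.625; result 0.60.

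| w | k = 0.1 | k = 0.25 | k = 0.5 |
|---|---|---|---|
| 1 (drug inhalation only) | 0.995 | 0.970 | 0.894 |
| 0.75 | 0.991 | 0.947 | 0.809 |
| 0.5 | 0.980 | 0.882 | 0.600 |

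The row w = 1 is what anchoring to the second inhalation would give. In the column k = 0.1 the rows barely differ. In the column k = 0.5, anchoring raises 0.600 to 0.894 if the participant would otherwise weight both periods equally. The loss therefore depends on how much air responses vary between people and on how participants weight the two periods. As written, the scheduled forms would not show either.

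**The case against.** The strongest reply has four parts.

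- **The plan does not rest on the questionnaires alone.** It pairs them with ratings made in the scanner, and it speaks of interpreting differences in brain activation, not of comparing questionnaire scores between conditions. This stands. A reader might infer that the across-condition use is impossible; the documents do not support that, because the use is assigned to two sources jointly. However, the second source is undefined, and participants are asked to avoid jaw movement during scanning, so the response method also needs stating.
- **The named analyses are correlations between participants.** One score per participant is enough to compute them. This stands too. The weakness lies in what the score means.
- **The forms are not shown.** A separate retrospective form for each scan would fit the text. A reader might infer that there is exactly one score and no air value for any participant, but that is an inference. Nothing instructs separate forms either, and if they are intended, one sentence should say so.
- **Participants probably know which inhalation was the drug.** They have at least 10 lifetime hallucinogen uses, have already met the dose in the first session, and are asked about subjective effects, not comfort. This makes a large air contribution less likely, though it does not remove the ambiguity that the instructions create. The analysis section also does not say which session's score is used, and the first-session questionnaires are tied to the drug. They describe a different administration from the one imaged.

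**Conclusion.** The point holds as a fault in the recall period. Followed as written, the scan-day forms do not separate air from salvinorin A, while the objective and the planned correlation call for the response to salvinorin A. The correlation remains computable, and the primary outcome is untouched.

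The size is unknown. Under the assumed values it ranges from negligible (0.99 against 0.995) to substantial (0.60 against 0.894), and it is small if air responses vary little. The illustration assumes that D and P are independent and that the form is answered for the whole stay.

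It is tempting to read the share of scanner time after salvinorin A inhalation as a measure of contamination. The documents do not support this: minutes are not score weight, and the schedule's setup entry at -40 begins with arrival at the MRI suite, before the participant is in the magnet.

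The change is worth making because it costs almost nothing and the information cannot be recovered later.

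**What to change.** 1. In the narrative on the second experimental session day and in the schedule entry at 25 minutes, replace the whole-stay recall period with *the second inhalation only*. This does not disclose what the inhalation contained.
2. Under Statistical analysis of behavioral data, name that second-inhalation score as the subjective variable correlated with the drug-minus-air imaging measure.
3. For the across-condition use, choose one of two routes:
   - If questionnaire data are to support it, add a brief version of the same items for *the first inhalation only*, preferably asked verbally at the existing check between the scans. Recall after the drug scan may be coloured by the drug experience.
   - Otherwise, state that this use rests on the ratings made in the scanner. Define those ratings (item, time points, and a response method compatible with the instruction to keep still) and enter them in the schedule.

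Cost: changed instructions on existing forms and, if the first-inhalation version is added, a few extra minutes outside BOLD acquisition. If that version is asked only after the drug scan, it carries recall error, which would pass into any second-minus-first difference. For that reason the second-inhalation score is the safer variable for the correlation.

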Inhalation device: The inhalation delivery system (i.e. pipe) is made of glass. The part of the glass pipe which will hold the salvinorin A will be a 5 ml round bottom chemistry flask meeting American Society for Testing and Materials (ASTM) specification E438 for Type I, Class A borosilicate glass. The non-ferromagnetic tubing attached to the inhalation delivery system will be polytetrafluoroethylene (PFTE) tubing, which meets FDA standard for food contact, has a high maximum working temperature (260° C, which is higher than the 244-245° C vaporization point of salvinorin A), and does not thermally degrade until temperatures greater than 400° C. The tubing will be 0.635 cm inner diameter, and up to 400 cm in length. The same tubing will be used for a given subject or a set of new tubing will be used between drug administrations. Tubing will not be cleaned with solvents.

A label will be prepared for each test dose and affixed to the neck of the 5mL round bottom flask containing the dose. This label will be removed immediately prior to heating the flask for drug administration. Each dose will be labeled with subject name, date, session number, pharmacy compounding number, dose of salvinorin A, and a statement that the drug is limited to investigational use only.

Study Statistics

Primary outcome variable: The primary outcome measures for this study will consist of changes in activity and connectivity of brain regions during the acute effects of salvinorin A, compared to the preceding period after inhalation of the placebo condition (inhaled air).

Secondary outcome measures: The secondary outcome measures will include a range of subjective measures described below.

Subject-rated overall drug strength: Volunteers will be prompted to verbally rate the overall drug strength on an 11-point scale (0 – none, no effect to 10 – extreme, strongest imaginable) at various

time points (e.g., 1, 2, 3, 4, 5, 10, 15, 20, 25, 30, and 45 minutes after each drug inhalation) during the first experimental drug session day.

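### The primary imaging outcome is an open set of activity and connectivity changes with no named quantity, test or error control, and the power claim does not apply to the analysis described

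*Combined protocol and SAP*

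**What the plan says.** The Primary outcome variable paragraph under Study Statistics reads: "The primary outcome measures for this study will consist of changes in activity and connectivity of brain regions". The contrast is within participant, the salvinorin A scan against the air scan that precedes it. No region, network, connection or summary measure is singled out.

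MRI data analyses has two sentences. The first refers to standard preprocessing. The second begins "The time course of brain regions in standard brain atlases", gives two atlases as examples, and says that the time courses "will be extracted and submitted to functional connectivity analysis". No analysis of regional activity is described. No test statistic, threshold or correction appears there or elsewhere for the imaging outcome. The only test named in the plan is a paired t-test for outcomes measured at screening and at one week.

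Alpha appears only under Sample size, and twice. The first use is for behavioural ratings: "and an alpha of 0.05, 6 volunteers would be sufficient to detect effects on ratings of drug intensity with 95% power". The second is for imaging: "For similar parameters, including an effect size of 0.89, alpha of 0.05, and 80% power, 21 participants are necessary to power an ROI-based analysis". From this the plan concludes that "the proposed study of 20 participants would be powered to detect clinically significant differences in brain activity". The same section says that the effect sizes come from behavioural and not imaging measures.

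**The concern.** A primary analysis needs a stated quantity and a stated rule for calling it positive. Here the outcome covers two kinds of measure over an unspecified set of regions, and the analyst still has to choose the atlas, the measure, the test and the threshold. If those choices follow sight of the data, the chance of a false positive cannot be stated.

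The power statement does not fill the gap. It concerns ROI activity, while the analysis described is connectivity. It also uses alpha 0.05 with no allowance for a family of tests. A reader would take the 20 participants to be adequate for the primary outcome, and the documents do not show that.

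**Working it through.** **Inputs from the documents.** Sample size section: d = 0.89, alpha 0.05, 80% power, 21 participants for an ROI-based activity analysis, 20 planned. Primary outcome variable paragraph: paired contrast.

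**Assumptions.** The documents give no region count R, so I use 10, 20, 100 and 300. They do not say whether 0.89 is a paired or a between-group standardised difference, so I show both. Tests are two-sided.

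**Step 1: the plan's own figure.** The two-group t-test has noncentrality d × √(n/2) on 2n − 2 degrees of freedom. With n = 21 this is 0.89 × √10.5 = 2.88 on 40 df, and power is 80.3%. With n = 20 it is 0.89 × √10 = 2.81 on 38 df, and power is 78.3%. So 21 is matched by one uncorrected two-group test with 21 per group. The plan cites a published recommendation and shows no formula, so the match does not prove how 21 was obtained.

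The paired test has noncentrality d × √n on n − 1 df. With n = 20 this is 0.89 × √20 = 3.98 on 19 df, and power is 96.5%. On this reading 12 participants would give 80%. Neither reading includes a correction for several tests.

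**Step 2: size of the family.** R regions give R(R − 1)/2 connections: 45 for R = 10, 190 for R = 20, 4,950 for R = 100 and 44,850 for R = 300.

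**Step 3: power and chance findings.** The Bonferroni threshold for M tests is 0.05/M. Power is for one named effect of d = 0.89 at that threshold. The last column is 0.05 × M, the expected number of chance findings if every test were run at an uncorrected 0.05 and the drug had no effect.

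| Tests M | Threshold 0.05/M | Power, paired, n = 20 | Power, two-group formula, n = 20 per group | Expected chance findings, uncorrected |
|---|---|---|---|---|
| 1 | 0.05 | 96.5% | 78.3% | 0.05 |
| 2 | 0.025 | 92.9% | 68.4% | 0.1 |
| 8 | 0.00625 | 80.2% | 47.7% | 0.4 |
| 45 (R = 10) | 0.00111 | 56.7% | 26.1% | 2.25 |
| 190 (R = 20) | 0.000263 | 36.5% | 14.1% | 9.5 |
| 4,950 (R = 100) | 0.0000101 | 8.5% | 2.6% | 247.5 |
| 44,850 (R = 300) | 0.00000111 | 2.4% | 0.7% | 2,242.5 |

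The expected counts hold whatever the correlation between tests. If the 45 tests at R = 10 were independent, the chance of at least one false positive would be 1 − 0.95^45 = 90%. The problem does not need a large atlas.

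**Step 4: the larger effect in the documents.** The plan also cites an effect equivalent to d > 4 for rated drug strength under salvinorin A. At d = 4, paired, n = 20, power is close to 100% for every family in the table.

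**The case against.** The plan is silent on thresholds and does not prescribe uncorrected testing. A reader might infer that every region and every atlas connection will be tested separately at 0.05, that hundreds of chance findings will follow, and that the trial cannot fail. The documents do not support that. They do not say that connections are tested one by one, and 0.05 is given only as a sample-size input. A count above 100 needs at least 64 regions (0.05 × 64 × 63/2 = 100.8), and the documents give no region count. This part of the objection stands.

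A reader might also infer a strict choice between uncontrolled false positives and lost power. That does not follow either. False discovery rate, permutation and network-level methods lie between the two. Power would also survive Bonferroni if imaging effects came near d = 4. But that figure is behavioural, and the plan itself sizes on 0.89 as the more conservative value. A large true effect also does nothing to control error on connections that the drug leaves unchanged.

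Finally, this is a 20-person mechanistic study, where some exploration is expected. That is a reason to label exploratory results as such. It does not justify calling an undefined set primary and stating that it is powered.

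**Conclusion.** The concern holds in this form: no primary imaging quantity, test, threshold or multiplicity control is stated, so the false-positive rate of the primary analysis is undefined. The power statement concerns ROI activity, matches only a single uncorrected test, and does not carry over to atlas-wide connectivity.

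The size depends on assumptions. If 0.89 is a paired standardised difference and Bonferroni is used, power at n = 20 falls from 96.5% for one test to 57% for 45 connections and 8.5% for 4,950. Under the formula that matches 21, power starts at 78.3% and is already 68% for two tests. A reader of the table might conclude that 20 participants secure 80% power for a family of up to 8 tests. That holds only on the paired reading; the two-group formula gives 48%, and the documents do not say which reading applies. On either reading, 0.89 comes from psilocybin drug-intensity ratings and not from any imaging measure.

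**What to change.** Before any scan is analysed, amend Primary outcome variable, Sample size and MRI data analyses as follows.

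1. Name one atlas and a small primary family of named quantities. Because the primary objective covers both activity and connectivity, either include both or state openly that one becomes secondary. If activity stays, describe how it will be analysed.
2. Test salvinorin A minus air with a paired sign-flip permutation test on the maximum |t| over the family, at two-sided family-wise 0.05. State the assumption that the differences are symmetric about zero under the null. Since air always comes first, the test controls error for the difference between the scans and does not separate drug from order.
3. Make other region-level and connection-level results secondary under the same max-|t| control, and use the other atlas as a sensitivity analysis.
4. Restate the power sentence as applying to a single ROI activity test, or recompute it at the corrected threshold. Say whether 0.89 is a paired or a between-group effect and that it comes from behavioural ratings. Do not promise 80% power for any family size on the present evidence.

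This takes wording and a choice of quantities, with no new data. The cost is that fewer single-connection findings will be declared and some measures lose primary status.

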Fahn-Tolosa-Marin Tremor Rating Scale (TRS; Fahn et al., 1993): The TRS, which was used to classify resting and kinetic tremor severity in our dose-effects study of salvinorin A (Johnson et al., 2011), will be assessed at 15 and 30 minutes after salvinorin A administration during the first experimental drug session day. At these time points, study staff will visually assess kinetic tremor intensity as the participant bends both of his or her extended arms to touch middle finger to nose. Study staff will also rate the magnitude of resting tremor during the time interval leading up to the assessments of kinetic tremor (i.e., 0-15 min, 15-30 min) by closely observing the participant. Those who exhibit significant resting tremor during the first experimental session day that is determined to likely invalidate MRI data collection will not continue to the second experimental session day.

Statistical analysis plan

Sample size: Since no brain imaging data are available to directly assess the effects of salvinorin A on human brain activity, power analyses were calculated based on behavioral data from previous investigations in our laboratory that included a range of doses of the classic hallucinogen psilocybin (Griffiths et al., 2011), and a previous investigation in our laboratory that included a range of doses of salvinorin A (Johnson et al., 2011). Psilocybin dose produced large increases on drug intensity ratings ($d = 0.89$, where 0.2 represents a small effect, 0.5 represents a medium effect, and 0.8 represents a large effect), and salvinorin A dose (Johnson et al., 2011) exerted a very large effect on the area under the curve of rated drug strength ($\eta^2 = 0.81$, where 0.02 represents a small effect, 0.13 represents a medium effect, and 0.25 represents a large effect). However, these are behavioral, and not brain imaging, outcome measures.

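### The sample-size paragraph calls 21 participants necessary for the imaging analysis and then calls 20 powered; the step between is unsupported by the plan's only imaging sample size

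*Combined protocol and SAP*

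**What the plan says.** The Sample size section of the Statistical analysis plan starts from two behavioural effects seen in the sponsor's own laboratory: d = 0.89 for psilocybin on drug-intensity ratings, and eta-squared = 0.81 (given as d > 4) for salvinorin A on rated drug strength. It adds a caution: "However, these are behavioral, and not brain imaging, outcome measures".

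It then proceeds in this order:

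1. It chooses the smaller effect: "Using the lower (more conservative) of the two effect sizes from our previous psilocybin and salvinorin A studies". At this d and alpha 0.05 it says 6 volunteers give 95% power for the drug-intensity ratings.
2. For imaging, at d = 0.89, alpha 0.05 and 80% power, it takes a number from a cited methods paper: "21 participants are necessary to power an ROI-based analysis of effects on brain activity similar to behavioral effects of psilocybin".
3. It adds: "Far fewer participants would be necessary to detect effects similar to the behavioral effects of salvinorin A, though no specific sample size recommendations". The sentence goes on to say that the paper made none for so large an effect.
4. It concludes: "Thus, the proposed study of 20 participants would be powered to detect clinically significant differences in brain activity between placebo and salvinorin A conditions".

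Recruitment and screening sets the 20 as volunteers who finish the study with full data, out of up to 200 consented. The primary outcome variable (Study Statistics) and the description of the second experimental session day make the contrast within-person: each participant has a placebo scan followed by a salvinorin A scan.

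**The concern.** The only imaging sample size in the plan is 21, described as necessary, and the study will have 20. The concluding sentence is worded as a consequence of what precedes it, but it does not follow from that figure. Because 20 is already the analysable number, there is no dropout allowance to absorb the difference.

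This sentence justifies the sample size for the primary outcome. As it stands, a reader cannot tell what size of effect 20 completers can detect. The claim is attached to clinically significant differences rather than to an effect size, no test is named for the primary contrast, and d is not defined. A standardised difference can be divided by the SD of the within-person differences or by the raw SD, and whether 20 reaches 80% power can depend on which is meant.

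**Working it through.** **Inputs.** From the Sample size section: d = 0.89, alpha 0.05, 80% power, 21 necessary, 20 planned; 6 volunteers for 95% power on ratings; eta-squared = 0.81. From Recruitment and screening: 20 are completers. Assumed, because not stated: two-sided tests unless noted, and t-tests with power from the noncentral t distribution.

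**1. The plan's 21.** A two-sample t-test at d = 0.89 (noncentrality d × √(n/2), df = 2n − 2) gives 80.35% power at n = 21 per group and 78.3% at n = 20 per group. So 21 reproduces as a per-group number for independent groups. The match is numerical only; the plan attributes 21 to a cited paper and gives no formula.

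**2. Size of the one-participant gap, if 21 gives about 80%.** Since the derivation is unknown, three assumed routes are shown:

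| Assumed basis for 21 | Power at 21 | Power at 20 | Loss (points) |
|---|---|---|---|
| Two-sample t, d = 0.89 | 80.35% | 78.3% | 2.0 |
| Paired t, effective d = 0.643 | 80.0% | 77.8% | 2.2 |
| Paired t, d = 0.89, effective alpha 0.0047 | 80.0% | 76.8% | 3.2 |

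**3. The within-person contrast.** Let d_z be the mean within-person difference divided by the SD of those differences (noncentrality d_z × √n, df = n − 1). At d_z = 0.89:

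- n = 11: 75.8%; n = 12: 80.1%
- n = 18: 94.5%; n = 19: 95.6%; n = 20: 96.5%

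So 12 completers suffice for 80% power and 19 for 95%. At n = 20, 80% power corresponds to d_z = 0.66.

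**4. If 0.89 is instead standardised by the raw SD.** Then d_z = 0.89 / √(2(1 − r)), where r is the correlation between a person's two scans. The documents give no r, so these are assumed values at n = 20:

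- r = 0: d_z = 0.89/√2 = 0.629, power 76.1%
- r = 0.09: d_z = 0.89/√1.82 = 0.660, power 79.9%
- r = 0.5: d_z = 0.89/√1 = 0.89, power 96.5%

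On this reading 20 reaches 80% once r is about 0.09 or more.

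**5. The larger effect.** d = 2 × √(0.81/0.19) = 4.13, which agrees with the plan's d > 4. The conversion is sound. What is missing is any imaging sample size tied to it.

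**6. The 6 volunteers in the same paragraph.** A paired t-test at d_z = 0.89 and n = 6 has 42% power two-sided and 59% one-sided, against the stated 95%. For 95%, 19 are needed two-sided and 16 one-sided. Six would suffice only at d_z of about 1.87 (two-sided) or 1.58 (one-sided). Entering 0.89 as Cohen's f in a two-level repeated-measures ANOVA with an assumed correlation of 0.5 gives 93% at 6, which is close, but f is a different effect size from d.

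**The case against.** The strongest defence is that the paragraph argues by bracketing: 21 for a psilocybin-like effect, far fewer for an effect like that of the drug actually under study, so 20 is enough. Nor does the concluding sentence claim 80% power at d = 0.89. This stands far enough that the paragraph should not be called a flat contradiction. It does not rescue the conclusion. The bridging remark supplies no sample size, gives up the effect size just chosen for being conservative, and carries a behavioural effect over to imaging after the plan has warned that these are not imaging measures.

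A second defence is that 21 may be the wrong yardstick. It matches an independent-groups number, whereas this study compares each person with themselves. That is possible but cannot be settled from the documents. It is also an argument the plan does not make; if it is the reason for 20, the plan should say so.

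A reader might infer two stronger things. One is that the trial is underpowered. The documents do not support this: the gap is a single participant, and on a paired reading with d_z = 0.89 the power at 20 is well above 80%. The other is that the figure of 6 is a proven error. It does not reproduce with a paired t-test, but the plan states neither the test nor the definition of the effect size, so another definition might account for it.

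**Conclusion.** The conclusion that 20 participants are powered is unsupported by the plan's only imaging sample size. The shortfall is one participant: about 2 points of power, or 2 to 3 across the assumed derivations in the table, on the premise that 21 gives 80%. This is a minor reporting fault in the sample-size justification, not a design fault.

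That 20 falls below a number called necessary, with only an unquantified remark between them, rests on the text alone. The power figures rest on two-sided t-tests at alpha 0.05. The 96.5% further requires that 0.89 be standardised by the SD of the within-person differences; under the raw-SD reading, 20 falls just short of 80% when r is below about 0.09. All of these figures concern one uncorrected comparison. None describes the analysis under MRI data analyses, where time courses from atlas regions "will be extracted and submitted to functional connectivity analysis".

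**What to change.** Keep n = 20 and replace the concluding power sentence with one of these, not both:

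- **(a)** State that 20 completers is one below the cited 21, so 80% power at d = 0.89 is not quite met on that basis.
- **(b)** Rest the claim on the within-person design and state the test, the definition of d and the detectable effect. For example: with 20 completers, a single two-sided paired comparison of salvinorin A with placebo in one ROI, at alpha 0.05 without multiplicity correction, has 80% power for d_z = 0.66 (mean within-person difference over the SD of those differences); this does not cover the atlas-wide connectivity analysis. With (b), stop citing 21 as support unless it rests on the same definition of d.

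Option (b) is preferable because it needs nothing from the cited paper, but the plan must then name the ROI comparison it refers to. Under either option, put the stated effect size in place of the reference to clinical significance. In the same edit, check the figure of 6 volunteers for 95% power and state the test and the effect-size definition behind it.

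Raising the target to 21 completers would also remove the mismatch, but it costs another participant's sessions and scans to match a figure whose derivation is not shown.

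The cost is a few sentences of SAP wording, with no extra volunteers or scans. The downside is that the power claim becomes slightly less favourable under (a), or is limited to one uncorrected ROI comparison under (b).
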